### **5.3.3.3. Tumor assessments**

All investigation dates (eg, X-ray, CT scan) must be completed with day, month and year.

If there are multiple scan dates associated with an evaluation, ie, radiological assessments occur over a series of days rather than the same day, the choice of date of assessment could impact the date of progression and/or date of response. If there are multiple scan dates associated with an evaluation, the earliest of the scan dates associated with the evaluation will be used as the date of assessment.

If one or more investigation dates for an evaluation are incomplete but other investigation dates are available, the incomplete date(s) are not considered for calculation of the assessment date and assessment date is calculated as the earliest of all investigation dates (eg, X-ray, CT-scan).

If all measurement dates for an evaluation have no day recorded, the 1st of the month is used.

If the month is not completed, for any of the investigations for an evaluation, the respective assessment will be considered to be at the date which is exactly between the previous and the following assessment. If both a previous and following assessments are not available, this assessment will not be used for any calculations.

### **5.3.3.4. Date of start of new anti-cancer therapy**

Incomplete dates for start date of new anti-cancer therapy (drug therapy, radiation, surgery) will be imputed as follows and will be used for determining censoring dates for sensitivity efficacy analyses and in the derivation of the end of on-treatment period. PD date below refers to PD date by modified RECIST V1.1.

- The end date of new anti-cancer therapy will be included in the imputations for start date of new anti-cancer therapy. If the end date of new anti-cancer therapy is
  - completely missing then it will be ignored in the imputations below
  - partially missing with only year (YYYY) available then the imputations below will consider 31DECYYYY as the end date of the new anti-cancer therapy
  - partially missing with only month and year available then the imputations below will consider the last day of the month for MMMYYYY as the end date of the new anti-cancer therapy
- For patients who have not discontinued study treatment at the analysis cut-off date, last dose of study treatment is set to the analysis cut-off date in the imputations below.
- If the start date of new anti-cancer therapy is completely or partially missing then the imputed start date of new anti-cancer therapy is derived as follows:

- Start date of new anti-cancer therapy is completely missing

Imputed start date = min [max(PD date + 1, last dose of study treatment + 1), end date of new anti-cancer therapy]

- Only year (YYYY) for start of anti-cancer therapy is available

IF YYYY < Year of min [max(PD date + 1, last dose of study treatment + 1), end date of new anti-cancer therapy] THEN imputed start date = 31DECYYYY;

ELSE IF YYYY = Year of min [max(PD date + 1, last dose of study treatment + 1), end date of new anti-cancer therapy]

THEN imputed start date = min [max(PD date + 1, last dose of study treatment + 1), end date of new anti-cancer therapy]

ELSE IF YYYY > Year of min [max(PD date + 1, last dose of study treatment + 1), end date of new anti-cancer therapy]

THEN imputed start date = 01JANYYYY

- Both Year (YYYY) and Month (MMM) for start of anti-cancer therapy are available

IF

YYYY = Year of min [max(PD date + 1, last dose of study treatment + 1), end date of new anti-cancer therapy], AND

MMM < Month of min [max(PD date + 1 day, last dose of study treatment + 1 day), end date of new anti-cancer therapy]

THEN

imputed start date = DAY (Last day of MMM) MMM YYYY;

ELSE IF

YYYY = Year of min [max(PD date + 1, last dose of study treatment + 1), end date of new anti-cancer therapy], AND

```
MMM = Month of min [max(PD date + 1 day, last dose of study treatment + 1
day), end date of new anti-cancer therapy]
THEN
    imputed start date = min [max(PD date + 1 day, last dose of study treatment + 1
day), end date of new anti-cancer therapy]);
ELSE IF
    YYYY = Year of min [max(PD date + 1, last dose of study treatment + 1), end
date of new anti-cancer therapy], AND
    MMM > Month of min [max(PD date + 1 day, last dose of study treatment + 1
day), end date of new anti-cancer therapy]
THEN
    imputed start date = 01 MMM YYYY;
ELSE IF
    YYYY < Year of min [max(PD date + 1, last dose of study treatment + 1), end
date of new anti-cancer therapy]
THEN
    imputed start date = DAY (Last day of MMM) MMM YYYY;
ELSE IF
    YYYY > Year of min [max(PD date + 1, last dose of study treatment + 1), end
date of new anti-cancer therapy]
THEN
    imputed start date = 01 MMM YYYY.
```

## 6. ANALYSES AND SUMMARIES

Refer to Section 4 for definitions of analysis sets and Section 5.2 for general methodology.

### 6.1. Primary Endpoints

#### 6.1.1. Progression-free survival per modified RECIST v1.1

##### 6.1.1.1. Primary analysis

The following analyses will be based on the FAS using the strata assigned at randomization. PD below refers to PD by investigator assessment per modified RECIST v1.1. Tumor-related endpoints in this study will be based on RECIST v1.1 modified with respect to the definition of what constitutes PD as follows (Appendix 3 of the B9991016 protocol). Any of the following will constitute PD per modified RECIST v1.1:

- Locoregional disease progression per RECIST v1.1 which is subsequently confirmed by pathology. Pathologic confirmation of progression will verify that radiographic changes

represent true tumor progression and not radiation effects or non-malignant contrast enhancement;

- Locoregional clinically detectable progression that is confirmed by pathology;
- Surgical removal (salvage) of primary tumor with tumor present on final pathology;
- Salvage neck dissection >20 weeks (140 days) after completion of CRT with tumor present on final pathology;
- Metastatic (distant metastases) disease progression per RECIST v1.1. Confirmation of pathology is recommended unless medically contraindicated or lesion location too high risk for biopsy.

**Local failure** is defined as residual or recurrent viable tumor on pathologic evaluation from the site of original tumor location. Presence of tumor is required for declaration of a progression event which requires identification of viable tumor cells on final pathology. Tumor reappearing within the initial and immediately adjoining anatomical region of the primary will be considered local recurrence.

**Regional failure** is defined as residual or recurrent viable tumor on pathologic evaluation from the regional lymph node basins (eg, neck nodes). Presence of tumor is required for declaration of a progression event which requires identification of viable tumor cells on final pathology.

**Distant metastatic disease** is defined as new tumor identified at a site distant from the head and neck anatomic region or draining lymph nodes. Biopsy of any presumed distant metastatic disease is strongly recommended. A solitary, speculated lung mass/nodule is a second primary neoplasm and is not a disease progression event unless proven otherwise by biopsy in a patient with a smoking history. Multiple lung nodules/masses are considered distant metastases from the index cancer and constitutes a disease progression event unless proven otherwise by biopsy.

Irradiation of the primary tumor and radiographically enlarged lymph nodes is considered part of the treatment under investigation in this clinical trial and therefore these target lesions remain evaluable lesions for response assessment.

It is expected that the status of the primary tumor is assessed thoroughly at the beginning of the surgical procedure before undertaking nodal dissection. Presence of persistent disease at the primary site, confirmed by frozen section will be considered disease progression.

Neck dissection parameters are described in Section 3.4 of the B9991016 protocol and will consist of a selective neck dissection unless a cytologic sampling of the nodes that appear enlarged is negative. Positive neck specimens removed within 140 days after completion of CRT will be considered part of the initial treatment plan and not considered as failures of initial management; positive specimens upon neck dissection beyond 140 days will be considered regional failures.

Progression-Free Survival (PFS) is defined as the time from the date of randomization to the date of the first documentation of PD or death due to any cause, whichever occurs first. For example, the date of first documentation of PD when there is locoregional PD per RECIST v1.1 which is subsequently confirmed by pathology, will be the date of the locoregional PD per RECIST v1.1 rather than the date of pathology confirmation.

PFS data will be censored on the date of the last adequate tumor assessment or clinical evaluation for patients who do not have an event (PD or death); the analysis will consider any PD or death as an event regardless of the number of prior missing tumor assessments or clinical evaluations or timing of the event with respect to initiation of subsequent anti-cancer therapy.

The censoring and event date options to be considered for the PFS and DR analysis are presented in Table 9.

$$\text{PFS (months)} = [\text{date of event or censoring} - \text{date of randomization} + 1] / 30.4375$$

**Table 9. Outcome and Event Dates for PFS Analyses**

Scenario	Date of event/censoring	Outcome
No adequate baseline assessment and no PD and no death	Date of randomization	Censored
No adequate post-baseline tumor assessment or clinical evaluation and no death	Date of randomization	Censored
PD or death	Date of PD or death	Event
No PD and no death	Date of last adequate tumor assessment or clinical evaluation documenting no PD	Censored

The primary efficacy analysis will compare the PFS time between Arm A and Arm B, and will be performed using a 1-sided stratified log-rank test as described in Section 5.1.

The treatment effect will be estimated using a Cox's Proportional Hazard model stratified by the randomization strata to calculate the hazard ratio. Each stratum will define a separate baseline hazard function (using the 'STRATA' statement in SAS PROC PHREG), ie for the i-th stratum the hazard function is expressed as:  $h(i;t) = h(i,0;t) \exp(x\beta)$ , where  $h(i,0;t)$  defines the baseline hazard function for the i-th stratum and  $x$  defines the treatment arm (0=Arm B, 1= Arm A) and  $\beta$  is the unknown regression parameter.

Ties will be handled by replacing the proportional hazards model by the discrete logistic model (Ties=Discrete option in SAS PROC PHREG).

In order to account for the group sequential design in this study, the repeated CI (RCI) method (Jennison and Turnbull, 2000^11), will be used to construct the 2-sided RCIs for the hazard ratio at the interim and the final analyses of PFS.

In addition, the unadjusted 95% CIs for the hazard ratio will also be reported at the interim and the final analyses for PFS.

Kaplan-Meier estimates (product-limit estimates) will be presented by treatment arm together with a summary of associated statistics including the median PFS time with 2-sided 95% CIs. In particular, the PFS rates at 12, 24, 36, 48 and 60 months will be estimated with corresponding 2-sided 95% CIs. The CIs for the median will be calculated according to Brookmeyer and Crowley (1982) and the CIs for the survival function estimates at the time points defined above will be derived using the log-log transformation according to Kalbfleisch and Prentice (2002) (conftype=loglog default option in SAS Proc LIFETEST) with back transformation to a CI on the untransformed scale. The estimate of the standard error will be computed using Greenwood's formula.

Frequency (number and percentage) of patients with each event type (PD or death) and censoring reasons will be presented by treatment arm.

Reasons for censoring will be summarized according to the categories in Table 10 following the hierarchy shown.

**Table 10. PFS Censoring Reasons and Hierarchy**

Hierarchy	Condition	Censoring Reason
1	No adequate baseline assessment AND no PD AND no death	No adequate baseline assessment
2	No event and [withdrawal of consent date $\geq$ date of randomization OR End of study (EOS) = Patient refused further follow-up]	Withdrawal of consent
3	No event and lost to follow-up in any disposition page	Lost to follow-up
4	No event and [EOS present OR disposition page for any epoch after screening says patient will not continue into any subsequent phase of the study] and no adequate post-baseline assessment	No adequate post-baseline assessment
5	No event and none of the conditions in the prior hierarchy are met	Ongoing without an event

The PFS time or censoring time and the reasons for censoring will also be presented in a patient listing.

Frequency (number and percentage) of patients with each subtype of PD will be presented by treatment arm. The subtype of PD is collected in the eCRF and includes the following:

- Locoregional PD per RECIST v1.1 with pathologic confirmation
- Locoregional clinically detectable progression with pathologic confirmation
- Surgical removal (salvage) of primary tumor with tumor present on final pathology
- Salvage neck dissection >20 weeks after completion of SOC CRT with tumor present on final pathology

- Metastatic (distant metastases) disease progression per RECIST v1.1.

## **Time of Follow-Up for PFS**

A plot will be generated to compare planned and actual relative day of tumor assessments by treatment arm. A Kaplan-Meier plot for PFS follow-up duration will also be generated to assess the follow-up time in the treatment arms reversing the PFS censoring and event indicators. Kaplan-Meier estimates (product-limit estimates) will be presented by treatment arm together with a summary of associated statistics including the median time of follow-up for PFS with 2-sided 95% CIs. In particular, the rates at 12, 24, 36, 48 and 60 months will be estimated with corresponding 2-sided 95% CIs.

## **6.2. Secondary Endpoint(s)**

### **6.2.1. Safety endpoints**

Refer to Section 6.6.

### **6.2.2. Efficacy endpoints**

The following analyses will be based on the FAS by treatment arm unless otherwise specified.

Response endpoints (Best Overall Response [BOR], unconfirmed Objective Response [uOR], DR, TTR) will be analyzed separately based on investigator assessment per modified RECIST v1.1 and based on investigator assessment per programmatically derived standard RECIST v1.1 (Appendix 3).

#### **6.2.2.1. Overall survival**

The following analyses will be based on the FAS using the strata assigned at randomization.

Overall survival (OS) is defined as the time from the date of randomization to the date of death due to any cause. Patients last known to be alive will be censored at date of last contact.

$$\text{OS (months)} = [\text{date of death or censoring} - \text{date of randomization} + 1] / 30.4375$$

The primary analysis of OS will compare the OS time between Arm A and Arm B, and will be performed using a 1-sided stratified log-rank test as described in Section 5.1.

The treatment effect will be estimated using a Cox's Proportional Hazard model stratified by the randomization strata to calculate the hazard ratio. Each stratum will define a separate baseline hazard function (using the 'STRATA' statement in SAS PROC PHREG), ie for the  $i$ -th stratum the hazard function is expressed as:  $h(i;t) = h(i,0;t) \exp(x\beta)$ , where  $h(i,0;t)$  defines the baseline hazard function for the  $i$ -th stratum and  $x$  defines the treatment arm (0=Arm B, 1= Arm A) and  $\beta$  is the unknown regression parameter.

Ties will be handled by replacing the proportional hazards model by the discrete logistic model (Ties=Discrete option in SAS PROC PHREG).

In order to account for the group sequential design in this study, the repeated CI (RCI) method (Jennison and Turnbull, 2000^11), will be used to construct the 2-sided RCIs for the hazard ratio at the interim and the final analyses of OS.

In addition, the unadjusted 95% CIs for the hazard ratio will also be reported at the interim and the final analyses for OS.

Kaplan-Meier estimates (product-limit estimates) will be presented by treatment arm together with a summary of associated statistics including the median OS time with 2-sided 95% CIs. In particular, the OS rates at 12, 24, 36, 48, 60, 72, 84, and 96 months will be estimated with corresponding 2-sided 95% CIs. The CIs for the median will be calculated according to Brookmeyer and Crowley (1982) and the CIs for the survival function estimates at the time points defined above will be derived using the log-log transformation according to Kalbfleisch and Prentice (2002) (conftype=loglog default option in SAS Proc LIFETEST) with back transformation to a CI on the untransformed scale. The estimate of the standard error will be computed using Greenwood’s formula.

Frequency (number and percentage) of patients with an event (death) and censoring reasons will be presented by treatment arm. Reasons for censoring will be summarized according to the categories in Table 11 following the hierarchy shown.

**Table 11. OS Censoring Reasons and Hierarchy**

Hierarchy	Condition	Censoring Reason
1	No event and [withdrawal of consent date $\geq$ date of randomization OR End of study (EOS) = Patient refused further follow-up]	Withdrawal of consent
2	No event and [lost to follow-up in any disposition page OR data cut-off date – last contact date > 18 weeks]	Lost to follow-up
3	No event and none of the conditions in the prior hierarchy are met	Alive

The OS time or censoring time and the reasons for censoring will also be presented in a patient listing.

### **Time of Follow-Up for OS**

A Kaplan-Meier plot for OS follow-up duration will also be generated to assess the follow-up time in the treatment arms reversing the OS censoring and event indicators. Kaplan-Meier estimates (product-limit estimates) will be presented by treatment arm together with a summary of associated statistics including the median time of follow-up for OS with 2-sided 95% CIs. In particular, the rates at 12, 24, 36, 48, 60, 72, 84, and 96 months will be estimated with corresponding 2-sided 95% CIs.

### **6.2.2.2. Sensitivity analyses for progression-free survival**

The following sensitivity analyses will be performed to explore the robustness of the primary analysis results. These analyses are regarded as purely exploratory. The sensitivity analyses

will repeat the primary analysis (p-value, HR and 95% CIs) described in Section 6.1.1.1 with the modifications below:

- M1 - PFS per modified RECIST v1.1 following the censoring rules outlined in Table 12
- M2 - PFS per modified RECIST v1.1 on the PP analysis set using the censoring rules outlined in Table 9
- M3- PFS per modified RECIST v1.1 using an unstratified analysis using the censoring rules outlined in Table 9
- M4 - PFS per modified RECIST v1.1 using strata derived according to eCRF data instead of that entered in IRT using the censoring rules outlined in Table 9
- S0 - PFS with PD programmatically derived based on investigator assessment per standard RECIST v1.1 with the censoring rules defined in Table 13
- S1, S2, S3, S4 replicating the sensitivity analyses M1, M2, M3 and M4, respectively, for PFS with PD programmatically derived based on investigator assessment per standard RECIST v1.1. The censoring rules associated with S1 are outlined in Table 14
- S0\_B - PFS with PD based on Blinded Independent Central Review (BICR) assessment per standard RECIST v1.1 with the censoring rules defined in Table 13
- M1\_B - PFS with PD based on BICR assessment per standard RECIST v1.1 with the censoring rules defined in Table 12.

**Table 12. Outcome and Event Date for PFS Sensitivity Analysis (M1)**

Scenario	Date of Progression/Censoring	Outcome
No adequate baseline assessment	Date of randomization a	Censored a
PD or death 
 
- following at most one missing or indeterminate post-baseline tumor assessment or clinical evaluation, OR
 
- ≤ 36 weeks after the date of randomization
 
	Date of PD or death	Event
PD or death following two or more missing or indeterminate post-baseline tumor assessments or clinical evaluations b	Date of last adequate tumor assessment b or clinical evaluation documenting no PD prior to new anti-cancer therapy or missed assessments	Censored
No PD and no death		
New anti-cancer therapy given		
a If the patient dies ≤36 weeks after date of randomization, the death is an event with date on death date. b If there are no adequate post-baseline tumor assessments or clinical evaluations prior to the PD or death, then the time without adequate assessment should be measured from the date of randomization; if the criteria were met the censoring will be on the date of randomization		

**Table 13. Outcome and Event Date for PFS Sensitivity Analysis (S0)**

Scenario	Date of event/censoring	Outcome
No adequate baseline assessment and no PD and no death	Date of randomization	Censored
No adequate post-baseline tumor assessment and no death	Date of randomization	Censored
PD or death	Date of PD or death	Event
No PD and no death	Date of last adequate tumor assessment documenting no PD	Censored

**Table 14. Outcome and Event Date for PFS Sensitivity Analysis (S1)**

Scenario	Date of Progression/Censoring	Outcome
No adequate baseline assessment	Date of randomization a	Censored a
PD or death 
 
- following at most one missing or indeterminate post-baseline tumor assessment, OR
 
- <math>\leq 36</math> weeks after the date of randomization
 
	Date of PD or death	Event
PD or death following two or more missing or indeterminate post-baseline tumor assessments b	Date of last adequate tumor assessment b documenting no PD prior to new anti-cancer therapy or missed assessments	Censored
No PD and no death		
New anti-cancer therapy given		
a If the patient dies $\leq 36$ weeks after start date, the death is an event with date on death date. b If there are no adequate post-baseline tumor assessments prior to the PD or death, then the time without adequate assessment should be measured from the date of randomization; if the criteria were met the censoring will be on the date of randomization		

### Methods for evaluating the validity of model assumptions

The proportional hazards assumption will be checked visually by plotting  $\log(-\log(\text{PFS}))$  versus  $\log(\text{time})$  within each randomization stratum.

Schoenfeld residuals for the stratified Cox proportional regression model will be plotted to investigate graphically violations from the proportional hazards (PH) assumption; a non-zero slope is evidence of departure from PH. The PH assumption will be formally tested using Schoenfeld's residual test (Schoenfeld, 1980^18; Therneau & Grambsch, 2000^20). Large departures from PH will be evidenced by a p-value  $< 0.05$ .

If these show large departures from proportional hazards, then PFS by modified RECIST v1.1 will also be analyzed based on restricted mean survival time (RMST) differences (Zhang, 2013).

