## 9.1. Sample Size Determination

The study is designed to test the following hypotheses:

$$H_0: HR_{PFS}(A/B) \geq 1 \text{ versus } H_a: HR_{PFS}(A/B) < 1$$

Where  $HR_{PFS}(A/B)$  represents the hazard ratio (HR) for PFS in Arm A vs Arm B. A stratified log-rank test stratified by randomization stratification factors will be used for analysis of PFS.

Two hundred eighty-nine (289) PFS events will be required to have at least 90% power to detect a hazard ratio of 0.68 using a 1-sided log-rank test at a significance level of 0.025, and a 2-look group-sequential design with Lan-DeMets (O'Brien-Fleming)  $\alpha$ -spending function to determine the efficacy boundary and a Gamma Family (-7)  $\beta$ -spending function to determine the non-binding futility boundary.

The sample size of 640 patients for this study is determined based on the assumptions that the median PFS for patients in Arm B is 33 months and that combination treatment including avelumab (Arm A) is expected to increase the median PFS to  $\geq 48.5$  months, corresponding to a HR of  $\leq 0.68$  under the exponential model assumption.

The sample size further assumes a 15% drop-out rate within each treatment arm and a non-uniform patient accrual over a 22-month period. The data cutoff for the primary PFS analysis will occur after the target number of events has been reached and the last patient randomized in the study has been followed for at least 24 months after randomization.

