### 5.1.2. Decision rules

To protect the integrity of the study and to preserve the type I error rate, a fraction of alpha (0.0097) for PFS efficacy will be spent at the interim analysis and accounted for in the overall type I error rate if the interim analysis is performed exactly at the planned number of

PFS events. The nominal significance levels for the interim and final efficacy analyses of PFS will be determined by using the Lan-DeMets procedure with an O'Brien-Fleming stopping boundary. The overall significance level for the efficacy analysis of PFS will be preserved at 0.025 (1-sided).

Two analyses will be performed for PFS:

- 1) an interim analysis after all patients have been randomized in the study and at least 217 (75%) of the 289 PFS events have been documented per modified RECIST v1.1, and
- 2) the final analysis for PFS after all patients randomized in the study have been followed for 24 months and at least 289 PFS events have been documented per modified RECIST v1.1.

If the value of the test statistic for PFS exceeds the efficacy boundary for a comparison ( $z < -2.338$ ,  $p < 0.010$  if the IA is performed after exactly 217 events), then superiority of Arm A compared to Arm B could be declared. If the value of the test statistic for PFS exceeds the futility boundary ( $z > -0.728$ ,  $p > 0.233$  if the IA is performed after exactly 217 events), then the study may be stopped for futility.

Since the observed number of events at the interim analysis may not be exactly equal to the planned 217 PFS events, the efficacy and futility boundaries will be updated based on the actual number of observed events using the pre-specified  $\alpha$ - and  $\beta$ -spending functions. Therefore, the observed Z-test statistic at the interim analysis will be compared with the updated efficacy and futility boundaries.

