## **Restricted Mean Survival Time (RMST)**

The hazard ratio estimate from the Cox proportional hazard model is routinely used to empirically quantify the between-arm difference under the assumption that the ratio of the two hazard functions is constant over time. When this assumption is plausible, such a ratio estimate may capture the relative difference between two survival curves. However, the clinical meaning of such a ratio estimate is difficult, if not impossible, to interpret when the underlying PH assumption is violated (ie, the hazard ratio is not constant over time).

The RMST is a robust and clinically interpretable summary measure of the survival time distribution. Unlike median survival time, it is estimable even under heavy censoring. There is a considerable body of methodological research (eg, Royston and Parmar, 2011; Uno, Wei, et al., 2014; Zhang, 2013) about the use of RMST to estimate treatment effects as an alternative to the hazard ratio approach.

The RMST methodology is applicable independently of the PH assumption and can be used, at a minimum, as a sensitivity analysis to explore the robustness of the primary analysis results. However, when large departures from the PH assumption are observed, the log-rank test is underpowered to detect differences between the survival distributions for the treatment arms, and a test of the difference between the RMST for the experimental arm and the control arm may be more appropriate to determine superiority of the experimental arm compared to the control arm with respect to the time-to-event endpoint.

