#### **Methods for evaluating the validity of model assumptions**

The same methodology described in Section 6.2.2.2 for PFS will be used for OS.

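### The SAP makes the restricted-mean (RMST) analysis of PFS and OS conditional on a proportional-hazards check whose only numerical criterion is a p-value; make it unconditional

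*SAP*

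**What the plan says.** SAP 6.2.2.2, under the methods for evaluating model assumptions, lists three PH checks for PFS: log(-log) plots within each stratum, a plot of Schoenfeld residuals, and a formal Schoenfeld residual test. It then fixes the criterion: "Large departures from PH will be evidenced by a p-value" below 0.05. The next paragraph sets the trigger: "If these show large departures from proportional hazards, then PFS by modified RECIST v1.1 will also be analyzed based on restricted mean survival time (RMST)". No time transform for the test, no size of departure and no reading rule for the plots is given.

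The RMST subsection that follows states: "The RMST methodology is applicable independently of the PH assumption and can be used, at a minimum, as a sensitivity analysis". It also defines three truncation times (tau), a 95% CI and a one-sided p-value for the RMST difference.

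SAP 6.2.2.3 extends the arrangement: "The same methodology described in Section 6.2.2.2 for PFS will be used for OS".

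**The concern.** A p-value mixes the size of a departure with the number of events, so it cannot say whether the departure is large. A material departure can be non-significant at this event count, and a trivial one could be significant with many more events. The RMST analysis nevertheless hangs on that result, or on plots that each reader may judge differently.

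Non-proportionality is foreseeable. Avelumab is given before, during and for 12 months after CRT, and Protocol 5.5.1.1 says that responses to such agents can appear later than with cytotoxic drugs. The SAP itself warns that a hazard ratio is hard to interpret when PH fails.

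At stake is whether the reader of the final report sees a between-arm summary of PFS and OS that does not rest on PH, and whether its appearance depends on a pretest on the same data.

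**Working it through.** **Inputs from the documents.** 640 patients, 1:1 (SAP 5.1.1). Protocol 9.1: 289 "PFS events will be required to have at least 90% power to detect a hazard ratio of 0.68"; the test and the number of looks are specified as "using a 1-sided log-rank test at a significance level of 0.025, and a 2-look group-sequential design"; "the median PFS for patients in Arm B is 33 months", exponential; Arm A median 48.5 months; 15% dropout; non-uniform accrual over 22 months; at least 24 months of follow-up after the last randomization. SAP 5.1.2: interim at 217 events, where "a fraction of alpha (0.0097) for PFS efficacy will be spent at the interim analysis".

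**Assumptions, not in the documents.** Delay of 4 to 12 months with HR 1 before it; the post-delay HR; exponential dropout reaching 15% at month 33; accrual proportional to t^1.5; time transform for the test (Kaplan-Meier, KM, first, others as a range).

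**Step 1: reproduce the plan's own figures.**
- Fixed-design events: 4 × (1.960 + 1.282)² / (ln 0.68)² = 282.6, so 283.
- Lan-DeMets O'Brien-Fleming spending at 217/289 = 0.751: 2 × [1 − Φ(2.2414/√0.751)] = 0.0097, z = 2.338. Final one-sided level 0.0221.
- Group-sequential power at 289 events: 0.9016, against 0.9010 in SAP Table 7.

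The design arithmetic is right. The SAP gives no power for the Schoenfeld test, so that has to be simulated.

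**Step 2: the test.** At event k let p = n₁e^β / (n₁e^β + n₀), residual r = x − p, v = p(1 − p), and g = 1 − KM just before the event. Centre g as g* = g − Σgv/Σv. The statistic (Σg*r)² / Σg*²v is compared with 3.84. Under a constant HR of 0.68 it is non-significant in 93% to 96% of runs, so it is calibrated. Simulated calendar times of about 39 and 52 months for 217 and 289 events sit close to the 38 and 51 in Table 7.

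**Step 3: probability that the test is non-significant at 289 events** (KM transform; range over KM, rank, identity and log transforms in brackets).

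| Basis for post-delay HR | 4-month delay | 12-month delay |
|---|---|---|
| Average Cox HR near 0.68 | HR 0.63: 83% [76–85] | HR 0.47: 22% [21–33] |
| Arm A median kept at 48.5 months | HR 0.65: 86% [81–88] | HR 0.575: 50% [49–58] |
| Design HR after the delay | HR 0.68: 87% [83–89] | HR 0.68: 72% [72–78] |

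In the second row the HR is (33 − d)/(48.5 − d): 29/44.5 = 0.652 and 21/36.5 = 0.575. In the first row, intermediate delays give 70% (6 months, HR 0.60) and 53% (8 months, HR 0.555). Across the table the KM range is 22% to 87%. With a post-delay HR of 0.40 it is about 8% to 52%. Eight assumed strata change little: 84% at 4 months (HR 0.626) and 31% at 12 months (HR 0.50), against 30% unstratified for the latter.

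**Step 4: what RMST and landmark rates would show.** With λ = ln 2/33 = 0.0210 per month, S_B(t) = exp(−λt). After a delay d, S_A(t) = exp(−λd − λ·HR·(t − d)). The RMST difference is the integral of S_A − S_B from 0 to tau. SAP Table 7 puts the final PFS analysis at about month 51 under the alternative, so tau = 50 is used to represent the SAP's late values.

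| Scenario | RMST gain to 50 months | PFS difference at 12 months | PFS difference at 48 months |
|---|---|---|---|
| Constant HR 0.68 | 4.8 months | 6.5 points | 13.9 points |
| 6 months, then 0.60 | 4.5 months | 4.0 points | 15.4 points |
| 12 months, then 0.50 | 4.0 months | 0.0 points | 16.8 points |

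**The case against.** The strongest case against is that little is lost if RMST is not produced. SAP 6.1.1.1 requires, without condition and by arm, KM estimates, the median and PFS rates at 12, 24, 36, 48 and 60 months with CIs; 6.2.2.1 does the same for OS to 96 months. These need no PH assumption, and Step 4 shows that landmark rates expose a delay better than RMST does at a late tau. This stands. It rules out the inference that the HR would be the only PFS effect measure reported. What those outputs lack is a between-arm difference with a CI; of the planned PFS analyses, only RMST supplies one without PH.

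A reader might also infer the following, and the documents do not support it:

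- That a non-significant test is taken as proof of proportionality, or alone blocks RMST. The SAP never says what p ≥ 0.05 means, and the trigger refers to the plots as well as the test. A plot-based trigger has no rule, however, so it is discretionary.
- That one miss rate belongs to 289 events. The rate depends on the assumed delay, post-delay HR and time transform.
- That RMST would by itself reveal a delay. A contrast at an early tau such as 24 months would look sharper (1.5 months for a constant HR of 0.68, 0.5 for 12 months then 0.50), but the SAP sets tau near the end of follow-up.
- That the pretest threatens the primary conclusion. The RMST subsection does remark that an RMST test may suit a superiority decision better when PH fails badly. But 6.2.2.2 labels its analyses purely exploratory, and the decision rules in 5.1.2 rest on the log-rank test alone.

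**Conclusion.** The concern holds in a limited form. SAP 6.2.2.2 uses significance as its only numerical measure of a large departure and makes RMST conditional on it, against its own statement that RMST does not need PH. If the effect is delayed by 4 to 12 months, the test would be non-significant in roughly 22% to 87% of trials under post-delay effects tied to the design, and in about 8% to 52% if the post-delay HR is 0.40. These figures are for PFS at 289 events and rest on the assumed delay, post-delay HR, KM transform, accrual shape and dropout shape. They describe the formal test, not the chance that someone acts on a plot.

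The consequence is a gap in an exploratory sensitivity analysis. The log-rank decision, the stopping boundaries and type I error are untouched. This is a worthwhile improvement, not a defect that changes the trial's conclusion.

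**What to change.** In SAP 6.2.2.2, delete the clause that makes RMST conditional on large departures. Report the RMST difference with its 95% CI for PFS and OS at each analysis, labelled as a pre-specified exploratory sensitivity analysis, using the three tau rules already defined; they are written for PFS times, so spell out the OS equivalents in 6.2.2.3. At the PFS interim the table belongs with the unblinded output restricted by SAP 7.1. Keep the Schoenfeld test and the plots as description only, state the time transform, and drop the sentence equating a large departure with p < 0.05.

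The cost is a few sentences in the SAP and one more table per endpoint. The limitation to state beside it is that at the SAP's late tau values RMST summarises the overall gain and will not show a delay, so it should be read with the landmark rates.
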